Appendix 3. Cockcroft-Gault Formula

$C_{Cr} = [(140 - \text{age}) \times \text{weight}] / (72 \times S_{Cr}) \times 0.85$ (if female)

Abbreviations/ Units

C_{Cr} (creatinine clearance) = mL/minute

Age = years

Weight = kg

S_{Cr} (serum creatinine) = mg/dL

{Cockcroft 1976}

Appendix 4. Pregnancy Precautions, Definition for Female of Childbearing Potential, and Contraceptive Requirements

1) Definitions

a. Definition of Childbearing Potential

For the purposes of this study, a female-born subject is considered of childbearing potential following the initiation of puberty (Tanner stage 2) until becoming postmenopausal unless the subject is permanently sterile or has medically documented ovarian failure.

Women are considered to be in a postmenopausal state when they are at least 54 years of age with cessation of previously occurring menses for at least 12 months without an alternative cause. In addition, women younger than 54 years with amenorrhea of at least 12 months also may be considered postmenopausal if their FSH level is in the postmenopausal range and they are not using hormonal contraception or hormonal replacement therapy.

Permanent sterilization includes hysterectomy, bilateral oophorectomy, or bilateral salpingectomy in a female subject of any age.

b. Definition of Male Fertility

For the purposes of this study, a male-born subject is considered fertile after the initiation of puberty unless the subject is permanently sterile by bilateral orchidectomy or medical documentation.

2) Contraception Requirements for Female Subjects

a. Study Drug Effects on Pregnancy and Hormonal Contraception

Sacituzumab govitecan is contraindicated in pregnancy because a malformative effect has been demonstrated/suspected or is unknown, taking into consideration class effects and genotoxic potential. Based on the assessment of published data related to CYP450 enzyme inhibition and induction experiments for SN-38, efficacy of hormonal contraception is not expected to be impacted due to sacituzumab govitecan administration. A dedicated oral contraceptive drug-drug interaction clinical study has not been conducted. Refer to the latest version of the investigator's brochure for additional information.

b. Contraception Requirements for Female Subjects of Childbearing Potential

The inclusion of female subjects of childbearing potential requires the use of highly effective contraceptive measures that have a failure rate of less than 1% per year. A negative urine pregnancy test is required at baseline prior to study treatment administration on C1D1. The baseline urine pregnancy test does not need to be conducted if the screening pregnancy test was performed within 72 hours before study treatment administration on C1D1. Pregnancy tests will be performed thereafter on Day 1 of each treatment cycle starting from Cycle 2 through the last cycle and every 28 days after the last dose of study drug until the end of contraception requirement. If a urine pregnancy test is positive or equivocal, a confirmatory serum pregnancy test will be required.

Duration of required contraception for female subjects in this clinical study should start from the screening visit until 6 months after the last dose of study drug.

Female subjects must agree to 1 of the following contraceptive methods:

Complete abstinence from intercourse of reproductive potential. Abstinence is an acceptable method of contraception only when it is in line with the subject's preferred and usual lifestyle.

Or

Consistent and correct use of 1 of the following methods of birth control listed below:

- Nonhormonal intrauterine device (IUD)
- Hormonal IUD (must be used in conjunction with a barrier method)
- Bilateral tubal occlusion (upon medical assessment of surgical success)
- Vasectomy in the male partner (upon medical assessment of surgical success)

Or

Female subjects who wish to use a hormonally based method must use it in conjunction with a barrier method, preferably a male condom. Hormonal methods are restricted to those associated with the inhibition of ovulation. Hormonally based contraceptives and barrier methods permitted for use in this protocol are as follows:

- Hormonal methods (each method must be used with a barrier method, preferably male condom)
 - a) Oral contraceptives (either combined or progesterone only) (see [Appendix 5](#) for a list of UGT1A1 inducers and Section [6.5](#))
 - b) Injectable progesterone
 - c) Subdermal contraceptive implant
 - d) Transdermal contraceptive patch
 - e) Contraceptive vaginal ring
- Barrier methods (each method must be used with a hormonal method)
 - a) Male condom (with or without spermicide)
 - b) Female condom (with or without spermicide)

- c) Diaphragm with spermicide
- d) Cervical cap with spermicide
- e) Sponge with spermicide

Inclusion of methods of contraception in this list of permitted methods does not imply that the method is approved in any country or region. Methods should only be used if locally approved.

Female subjects must also refrain from egg donation, cryopreservation of germ cells, and in vitro fertilization during treatment and until the end of contraception requirement. Female subjects should be advised to seek advice of the Investigator about egg donation and cryopreservation of germ cells before treatment.

3) Contraception Requirements for Male Subjects

It is theoretically possible that a relevant systemic concentration of study drug may be achieved in a female partner from exposure of the male subject's seminal fluid and poses a potential risk to an embryo/fetus. Therefore, male subjects with female partners of childbearing potential must use condoms during treatment and until 6 months after the last dose of study drug. If the female partner of childbearing potential is not pregnant, additional highly effective contraception recommendations should also be considered.

Male subjects must also refrain from sperm donation, and/or cryopreservation of germ cells during treatment and until the end of contraception requirement. Male subjects should be advised to seek advice of the Investigator about sperm donation and cryopreservation of germ cells before treatment.

4) Unacceptable Birth Control Methods

Birth control methods that are unacceptable include periodic abstinence (eg, calendar, ovulation, symptothermal, postovulation methods), withdrawal (coitus interruptus), spermicides only, and lactational amenorrhea method. A female condom and a male condom should not be used together.

5) Procedures to be Followed in the Event of Pregnancy

Female subjects will be instructed to notify the Investigator if they become pregnant or suspect they are pregnant at any time from start of the study and throughout the study (including the post study drug follow-up period) or 6 months after the last dose of study drug, whichever is longer. Sacituzumab govitecan must be discontinued immediately upon consultation with the medical monitor.

Male subjects whose partner has become pregnant or suspects she is pregnant from start of study and throughout the study (including the post study drug follow-up period) or 3 months after the last dose of study drug, whichever is longer, must also report the information to the investigator. Instructions for reporting pregnancy, partner pregnancy, and pregnancy outcome are outlined in Section 10.2.4.

Appendix 5. UGT1A1 Inhibitors and Inducers

Inhibitors of UGT1A1	Inducers of UGT1A1
Amitriptyline	Carbamazepine
Atazanavir	Efavirenz
Dacomitinib	Ethinylestradiol
Dasabuvir	Lamotrigine
Deferasirox	Phenobarbital
Eltrombopag	Phenytoin
Enasidenib	Primidone
Erlotinib	Rifampicin
Flunitrazepam	Ritonavir
Flurbiprofen	Tipranavir
Fostamatinib	
Gemfibrozil	
Glecaprevir	
Indinavir	
Indomethacin	
Ketoconazole	
Nilotinib	
Ombitasvir	
Paritaprevir	
Pazopanib	
Pexidartinib	
Pibrentasvir	
Probenecid	
Propofol	
Regorafenib	
Rucaparib	
Silibinin	
Sorafenib	
Valproic acid

1. INTRODUCTION

The purpose of this Statistical Analysis Plan (SAP) is to describe the procedures and the statistical methods that will be used to analyze, and report results for study IMMU-132-14: “Open-label Rollover Study to Evaluate Long-term Safety in Subjects with Metastatic Solid Tumors that are Benefiting from Continuation of Therapy with Sacituzumab Govitecan”. This SAP incorporates the original version of the protocol, dated as 16Dec2019. The focus of this SAP is for the final analysis specified in the study protocol.

This SAP provides a comprehensive and detailed description of the objectives, definitions of endpoints, statistical and analytical methods used to evaluate the specified safety endpoints. There is no efficacy analysis for this study.

2. STUDY OBJECTIVES AND ENDPOINTS

2.1. Primary Objectives and Endpoints

The primary objective is to evaluate long-term safety in subjects with metastatic solid tumors that are benefiting from continuation of therapy with sacituzumab govitecan.

The corresponding endpoints are:

- Safety evaluated on adverse events and serious adverse events, laboratory assessments, study drug exposure and concomitant medications

3. STUDY OVERVIEW

3.1. Study Design

This is an open-label, longitudinal cohort, rollover study designed to evaluate long-term safety in subjects with metastatic solid tumors that are benefiting from continuation of therapy with sacituzumab govitecan. Only subjects who continue to receive clinical benefit from continuation of sacituzumab govitecan therapy and are tolerating therapy at the time of enrollment are eligible for this study. Subjects enrolled may continue to receive sacituzumab govitecan at the dose that they were receiving in the Immunomedics-sponsored parent study at the time of consenting to participate in this rollover study. No dose escalation beyond the dose the subject was receiving in the Immunomedics-sponsored parent study at the time of consenting to participate in this rollover study is permitted. No subject will receive more than 10 mg/kg dose of sacituzumab govitecan. Subjects may continue to receive sacituzumab govitecan until they experience toxicity, disease progression or withdrawal of consent, lost to follow-up, loss of clinical benefit, or sponsor termination of the study is documented. Subjects who continued to receive sacituzumab govitecan in the parent study after disease progression (PD), may continue to receive sacituzumab govitecan until there is no clinical benefit per treating physician's assessment.

3.2. Determination of Sample Size

The sample size of up to approximately 200 subjects assumes that 10-15% of subjects in any of the ongoing sacituzumab govitecan parent studies will rollover to this study upon closure of the parent study.

4. ANALYSIS POPULATION

The following analysis population will be used for analyses:

- All Treated Subjects: defined as all subjects who have received at least one dose of study drug. This analysis population will be used as the basis for essentially all safety analyses.

5. STATISTICAL METHODS AND ANALYSIS

5.1. General Statistical Considerations

Endpoints and analyses pertaining to the study's primary objectives will be conducted as prescribed in respective sections of this SAP. Any notable analyses, adjustments to analyses, or analyses not conducted due to lack of data or due to other technical constraints will be noted.

All safety analyses will be analyzed in the All Treated Subjects population and presented by a single arm. When deemed appropriate, it may also be presented by dose level, cancer types and histology. Same for subgroup analysis, it may also be conducted.

Continuous data will be summarized using descriptive statistics: n (number of subjects), mean, median, standard deviation, upper and lower quartiles, and range (minimum and maximum), unless otherwise specified. Categorical data will be summarized using counts and percentages. For summary statistics, the tables will be presented by a single arm sacituzumab govitecan. In general, individual subject listings will be provided to support the tables.

All calculations and analyses will be conducted using SAS version 9.2 or higher.

5.2. Previous Immunomedics (Parent) Study Information

A by-subject listing will be provided for all subjects enrolled into the study, including previous study protocol number, previous subject number, previous site number, last cycle received while on parent study, last dose of sacituzumab govitecan in parent study and date of last dose of sacituzumab govitecan in parent study. If available, the date of first dose of sacituzumab govitecan in parent study, number of dose reduction and each dose reduction date and reason in parent study will also be listed.

5.3. Subject Disposition

Disposition in terms of number of subjects enrolled into the study, treated, permanently discontinued from treatment and discontinued from study, and reasons for treatment or study discontinuation will be summarized for All Treated Subjects.

A by-subject listing for disposition will be provided for all subjects, including their Informed Consent dates, Protocol Number the subject is consented under, study discontinuation date, and whether they meet inclusion/exclusion eligibility.

For All Treated Subjects, a listing is provided to include the following: treatment status, treatment start/end date, reason for treatment discontinuation, study completion status, study end date and reason for study discontinuation.

5.4. Demographics

Demographics for All Treated Subjects will be summarized using descriptive statistics.

Individual subject listings will be provided to support the summary tables.

5.4.1. Demographics

Baseline demographic data summaries will include age, age by categories (<50, 50-65 and >65 years; <=65 vs >65 years), sex, race, ethnicity.

5.5. Prior, Concomitant Medications and Non-protocol Specific Procedures/Surgeries

5.5.1. Prior and Concomitant Medications

Prior and concomitant medications will be coded using the World Health Organization (WHO) Drug Dictionary. Prior medications include medications with a start and end date prior to first administration of study drug. Concomitant medications are those medications that were taken at any time while on study treatment, including medications that were started before first dose of study therapy but were ongoing at the time of first dose of study drug or that were initiated after first dose but prior to last dose. If an end date is missing or the medication is ongoing during sacituzumab govitecan treatment, the medication will be included as concomitant medications. Prior and concomitant medications will be summarized separately for All Treated Subjects by following the WHO Drug Anatomical Therapeutic Chemical (ATC) Classification and listed for All Treated Subjects.

A by-subject listing will be provided for All Treated Subjects.

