5.3. Criteria for Treatment Discontinuation

Subjects will discontinue the treatment under any of the following conditions:

- 1) Withdrawal of consent from further treatment with study drug
- 2) Lost to follow-up. Subjects will be considered lost to follow up when there is no response to two attempts one month apart by phone and a registered letter. After these 3 failed attempts, lost to follow-up will be documented
- 3) An adverse event (AE) that, in the opinion of the Investigator or the sponsor, contraindicates further dosing
- 4) Initiation of alternative anti-tumor therapy, including any investigational agent
- 5) Pregnancy
- 6) Disease progression with no evidence of clinical benefit
- 7) Loss of clinical benefit
- 8) Subject non-compliance
- 9) Sponsor terminates the study

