6.4. Concomitant Medications

Medications initiated prior to the first dose of study drug will be recorded as prior medications with medications initiated following receipt of the first dose of study drug until 30 days after treatment discontinuation will be captured as concomitant medications. Medication information will be entered in the appropriate eCRF with information regarding dose, indication, route of administration and dates of administration. Medications used for prophylaxis of anticipated study drug adverse events as outlined in the protocol should be documented with rationale for prophylactic intent.

Subjects must avoid the use of osteopathic traditional medicine and any other traditional medicine during the study.

No anti-cancer therapies, aside from the study drug are permitted during this study. However, palliative and/or supportive medications, such as pain medications, bone modifying-medications (bisphosphonates or denosumab), anti-emetics or anti-diarrheal medications, transfusions and growth factor support are allowed at the investigator's discretion. Palliative radiotherapy is permitted.

Treatment may be continued after completion of palliative radiotherapy. In this case, sacituzumab govitecan administration should be interrupted one week before the procedure and reinstated no earlier than two weeks after the procedure. In the event that a subject requires surgery, sacituzumab govitecan should be interrupted one week before the procedure if clinically feasible and dosing should be held for 2 weeks after the procedure. Dosing may resume thereafter if the subject is clinically stable. Extensive surgical procedures such as abdominal, cranial surgeries for example, may require suspension of dosing for 4 weeks before dosing may resume to allow for an adequate period for healing.

The study medical monitor must approve continuation of therapy with sacituzumab govitecan prior to resumption of dosing.

Subjects are allowed to receive the COVID-19 vaccine to reduce the risk and complications of COVID-19 infection. Details on the risk assessment and mitigation plan for concurrent administration of the COVID-19 vaccine are provided in [Appendix 2](#).

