7. METHODS FOR HANDLING MISSING DATA

The imputation for missing data in adverse events, concomitant medications and other prior therapies/procedures will be provided in a separate file.

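### SAP 5.5.1 leaves medications first started after the last dose, with a recorded end date, out of both medication summaries, although Protocol 6.4 classes them as concomitant for a further 30 days

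*SAP*

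**What the plan says.** SAP 5.5.1 sets up two categories, each with its own summary for All Treated Subjects.

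- **Prior:** "Prior medications include medications with a start and end date prior to first administration of study drug".
- **Concomitant:** drugs taken while the subject is on study treatment. The text names those already in use at the first dose and those "that were initiated after first dose but prior to last dose".
- **Fallback:** "If an end date is missing or the medication is ongoing during sacituzumab govitecan treatment, the medication will be included as concomitant medications".

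The same section provides a by-subject listing, with no date limit stated.

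Protocol 6.4 draws the line elsewhere: "medications initiated following receipt of the first dose of study drug until 30 days after treatment discontinuation will be captured as concomitant medications". Protocol Table 1 schedules concomitant medications across the whole study, and Protocol 11.3.3 says they will be summarized, with no narrower window given. SAP 2.1 names them within the safety evaluation. SAP Section 8 reports no change from the protocol's analyses.

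Two statements limit what can be concluded. SAP Section 1 says "This SAP incorporates the original version of the protocol, dated as 16Dec2019", and that version is not supplied. SAP Section 7 says "The imputation for missing data in adverse events, concomitant medications and other prior therapies/procedures will be provided in a separate file", and that file is not supplied either.

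**The concern.** The two SAP categories do not cover every medication that the protocol collects. A drug that is started and finished after the last infusion is too late for the prior group and also too late for the concomitant group, yet Protocol 6.4 calls it concomitant.

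The omission falls in a period that matters for safety. Both documents count adverse events as treatment-emergent through 30 days after the last dose (Protocol 11.3.3, SAP 6.2). An event in that month enters the AE tables, while a drug newly begun to treat it, if it has an end date, is missing from the medication table. A reader who compares the two tables would see the event without the treatment given for it. In a study whose only objective is long-term safety, the medication summary should cover the same period as the events, or say that it does not.

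**Working it through.** There is no planned figure to reproduce. The check applies each rule to one test record.

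**Illustrative dates (assumed, not from the documents).** First dose Day 1; last dose Day 100, also taken as the date of treatment discontinuation; a drug started on Day 105 and stopped on Day 110, both dates recorded.

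| Rule | Source | Test | Result |
|---|---|---|---|
| Prior | SAP 5.5.1 | start and end before Day 1; 105 > 1 | not met |
| Taken while on study treatment | SAP 5.5.1 | use between Day 1 and Day 100; 105 > 100 | not met |
| New start before the last dose | SAP 5.5.1 | start before Day 100; 105 > 100 | not met |
| Fallback | SAP 5.5.1 | end date missing, or in use during treatment; neither | not met |
| Concomitant | Protocol 6.4 | start after Day 1 and by 100 + 30 = Day 130; 105 ≤ 130 | met |

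So the SAP puts the record in neither summary, and the protocol calls it concomitant.

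**What on treatment means.** SAP 6.1 computes treatment duration as last dose minus first dose plus 1, here 100 − 1 + 1 = 100 days. It adds nothing after the last dose, so Day 105 lies outside treatment as the SAP measures it.

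**Comparison with the adverse-event window.** Suppose the drug was given for an event that began on Day 104. Since 104 ≤ 100 + 30 = 130, the event is treatment-emergent in both documents and is tabulated. The drug is not.

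**Width of the gap.** With the last dose as anchor, 130 − 100 = 30 days. This is a length of time, not an amount of medication use. The documents give no rate of new medication starts after the last dose, so no count of affected subjects or drugs can be derived.

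**Role of the end date.** With no end date, the fallback sentence read literally would make the same record concomitant. The imputation file may alter that, so the finding is confined to records with an end date.

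**After the change.** With the SAP window for new starts set at last dose plus 30 days, 105 ≤ 130 makes the record concomitant, and 105 > 100 marks it as a start after the last dose.

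**The case against.** The best defence is that Protocol 6.4 governs what goes on the eCRF and SAP 5.5.1 governs what goes in the table. A summary of on-treatment use, drawn from a wider collection period, is a legitimate choice, and the SAP's general phrase about use while on treatment already suggests it. Part of this stands: such a table would be acceptable if declared. But Protocol 6.4 also assigns the class, Protocol 11.3.3 promises a summary of concomitant medications without restricting it, and SAP Section 8 declares no departure.

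It can also be said that the SAP's examples of concomitant use are not exhaustive. They do not need to be for the gap to exist. The general rule still requires use during treatment, and a drug begun after the last dose does not meet it.

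On importance the defence is stronger. The by-subject listing should still show these drugs, concomitant medications are not among the three primary endpoints in Protocol 11.3.1, and SAP Section 6 does not list them among the safety presentations, although SAP 2.1 does. That is why the point is minor.

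A reader might infer a gap longer than 30 days, because Protocol 6.4 counts from treatment discontinuation, which could be a decision made some weeks after the last infusion. The rest of the protocol does not favour that reading. The end-of-treatment visit (Section 3.4) and AE collection (Section 10.2.2.2) are both set at 30 days from the last dose. Table 1 footnotes b and e use drug discontinuation and last dose for the same six-month follow-up. The wording should be settled, but 30 days is the figure the documents support.

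**Conclusion.** The point holds as a minor inconsistency, with moderate confidence. Followed as written, SAP 5.5.1 omits from both summaries any medication first started after the last dose that has a recorded end date. The supplied Protocol 6.4 classes those started within 30 days as concomitant. This assumes that treatment discontinuation in Protocol 6.4 means the last dose. The effect is confined to the descriptive medication summary; AE, SAE and laboratory results are unaffected.

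Three stronger conclusions are not supported.

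- **That the SAP contradicts the protocol it was written from.** It rests on the version of 16Dec2019, which cannot be checked here. The SAP may simply not have been updated.
- **That subsequent cancer treatment is being hidden.** Protocol 6.4 says "No anti-cancer therapies, aside from the study drug are permitted during this study", and Protocol 5.3 makes "Initiation of alternative anti-tumor therapy, including any investigational agent" a reason to stop study treatment. Nothing in these passages shows a separate defect in how such therapy is reported.
- **That records without an end date are misclassified.** The fallback sentence gives no start-date limit, but the imputation file may supply one.

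**What to change.** In SAP 5.5.1, extend the window for newly started medications to last dose plus 30 days, matching the treatment-emergent AE window. Flag medications first started after the last dose, or show them in a separate row, so that on-treatment use stays distinct. If an on-treatment summary alone is intended, state this as a departure in SAP Section 8 and keep the separate row.

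At the next protocol amendment, use the same anchor date in Protocol 6.4 and reconcile it with Table 1, which schedules concomitant medications across the whole study and gives no 30-day limit.

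The cost is one SAP definition, one programmed flag and one extra table row. No new data are needed, since Protocol 6.4 already has these medications entered on the eCRF.
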